8.1.4 Monitoring of dose administration

Patients will be monitored before, during and after the infusion of durvalumab. Patients are monitored (pulse rate, blood pressure) every 30 minutes during the infusion period (including times where infusion rate is slowed or temporarily stopped).

In the event of a ≤Grade 2 infusion-related reaction, the infusion rate of study drug may be decreased by 50% or interrupted until resolution of the event (up to 4 hours) and re-initiated at 50% of the initial rate until completion of the infusion. For patients with a ≤Grade 2 infusion-related reaction, subsequent infusions may be administered at 50% of the initial rate.

Acetaminophen and/or an antihistamine (e.g., diphenhydramine) or equivalent medications per institutional standard may be administered at the discretion of the investigator. If the infusion-related reaction is Grade 3 or higher in severity, study drug will be discontinued. The standard infusion time is one hour. If there are interruptions during infusion, the total allowed time from infusion start to completion of infusion should not exceed 8 hours at room temperature (otherwise a new infusion preparation is required). For management of patients who experience an infusion reaction, please refer to the toxicity and management guidelines in Appendix 1.

As with any antibody, allergic reactions to dose administration are possible. Appropriate drugs and medical equipment to treat acute anaphylactic reactions must be immediately available, and study personnel must be trained to recognize and treat anaphylaxis. The study site must have immediate access to emergency resuscitation teams and equipment in addition to the ability to admit patients to an intensive care unit if necessary.

8.2 Carboplatin and etoposide chemotherapy

8.2.1 Formulation/packaging/storage

Commercially available drugs will be used. The drugs will be stored according to label.

All patients are to receive four courses of carboplatin (area under the curve (AUC) 5 mg/ml per min, Calvert's formula) iv on day 1 plus etoposide 100 mg/m² BSA iv day 1 followed by etoposide 200 mg/m² po or etoposide 100 mg/m² BSA IV days 2-4. Courses are administered every 3 weeks until a maximum of four courses.

BSA is calculated according to the formula by Dubois and Dubois: BSA=0.007184 x weight $^{0.425}$ x height $^{0.725}$. It is recommended to consider capping the dose at a BSA of 2.2 m².

Calvert's formula: carboplatin dose (mg) = AUC (mg ml-1 min) x [GFR (ml/min) + 25 (ml/min)

For most patients, GFR/creatinine-clearance will be calculated according to the Cockroft-Gault formula. For patients with a body weight falling below 30 kg or a serum-creatinine below the lower normal value, creatinine-clearance should be measured by 24-hour urine collection.

It is recommended to reduce the etoposide-dose by 25% if creatinine-clearance is below 50 mg/minute. The use of G-CSF is allowed.

8.2.2 Product preparation and administration

According to local routines. Suggested preparation and administration of carboplatin plus etoposide:

Day 1:

- Carboplatin is diluted in 500 ml 5% glucose and infused over 30 minutes
- Etoposide is diluted in 500 ml 0.9% NaCl and infused over 30 minutes

Day 2-4:

• Half the etoposide-dose is taken orally in the morning, half the dose in the evening. The tablets are

taken with a glass of water. If etoposide is given IV, it will be administered as on Day 1.

8.2.3 Suggested antiemetic medication (carboplatin)

Day 1:

 Ondansetron 16 mg PO or IV plus dexamethason 8 mg PO or IV (or equipotent dose of other corticosteroid) 1 hour before infusion of chemotherapy commences

Day 2-3:

Dexamethason 8 mg PO (or equipotent dose of another corticosteroid)

Other antiemetic therapy may be administered according to local routines.

8.2.4 Recommendations before a new course of chemotherapy:

- All grade 3-4 adverse events should have resolved to grade 0-2 or to the same level as before the preceding course of chemotherapy
- ANC ≥ 1.5 x 10⁹/L and platelets ≥ 100 x 10⁹/L. Lower values might be acceptable if the nadir-phase has passed.
- Creatinine < 125 μmol/litre (if creatinine ≥ 125 μmol/litre, cisplatin should be replaced with carboplatin)

8.2.5 Suggestions for dose adjustments:

- In case of grade 4 neutropenia (< 0.5 x 10⁹/L), grade 4 thrombocytopenia (< 50 x 10⁹/L) or febrile neutropenia (< 1.0 x 10⁹/L, fever and treatment with antibiotics) after the preceding course, it is suggested to reduce the doses for the next course to 80% of the preceding course.
- If ANC < 1.5 x 10⁹/L or platelets < 100 x 10⁹/L on day 22 (day for the next course), it is suggested to delay the next course until resolution of the cytopenia. A dose reduction of 20% is suggested if a course is postponed more than a week.
- If a course is postponed more than three weeks, the chemotherapy should be discontinued.

8.2.6 Duration of treatment and criteria for treatment through progression and for retreatment

Maximum 4 courses of chemoimmunotherapy will be administered. Durvalumab treatment will then continue until PD and need for other treatment, unacceptable toxicity or patients wish to discontinue.

Chemotherapy should be discontinued if a course is postponed more than three weeks, and may be discontinued earlier if severe, unacceptable, toxicity considered to be due to the chemotherapy occurs. Patients may continue durvalumab regardless of the number of chemotherapy courses completed provided the criteria for discontinuation of durvalumab are not met.

Chemo- and/or immunotherapy will be discontinued if RECIST 1.1-defined radiological progression and need for other treatment occur. Other reasons for discontinuation include unacceptable toxicity, withdrawal of consent, or patient's wish.

During the treatment period, patients who are clinically stable at an initial RECIST 1.1-defined PD may continue to receive study treatment at the discretion of the Investigator and patient as long as they are deemed to be receiving clinical benefit. In case, a follow-up scan is to be collected after the initial RECIST 1.1-defined PD, 4-6 weeks after the prior assessment of PD for confirmation of PD and to ensure that potentially rapid progression of relapsing SCLC is revealed within a reasonable timeframe to ensure that patients may be offered other treatment for PD.

Patients with PD who continue to receive IP at the discretion of the Investigator should undergo image acquisitions and tumor assessments according to the regular schedule for the duration of treatment.

Patients with rapid tumor progression or with symptomatic progression that requires urgent medical intervention (e.g. CNS-metastasis, respiratory failure due to tumor compression, or spinal cord compression) will usually not be eligible for continuing durvalumab treatment. If a general disease control has been achieved, and oligometastatic progression occurs, exceptions may be considered after discussing with the Chief Investigator.

For all patients who are treated through progression and for patients who are restarting

durvalumab (alone or in combination with chemotherapy), the Investigator should ensure that:

- The patient does not have any significant, unacceptable, or irreversible toxicities that indicate continuing treatment will not further benefit the patient. The patient may not have experienced a toxicity that required permanent discontinuation of study treatment.
- There is absence of clinical symptoms or signs indicating clinically significant disease progression accompanied by a decline in WHO/ECOG performance status to >1
- There is absence of rapid disease progression or threat to vital organs or critical anatomical sites (e.g. CNS-metastasis, respiratory failure due to tumor compression, or spinal cord compression) requiring urgent alternative medical intervention
- The patient still fulfills the eligibility criteria for this study (see 7.1) with the exception of inclusion criteria 8, 9, 11 and 12 and exclusion criteria 3 and 8. Patients must agree to restart durvalumab therapy.
- The patient has not received an intervening systemic anticancer therapy after their assigned treatment discontinuation.
- The patient has had a retreatment baseline tumor assessment within a maximum of 28 days
 prior to restarting their assigned treatment; all further scans should occur with the same
 frequency as during the initial 12 months of treatment (relative to the date of restarting
 treatment) until study treatment is stopped (maximum of 12 months of further treatment).

Patients who the Investigator determine may not continue treatment after RECIST 1.1-defined PD will be followed for survival. Patients who have discontinued treatment due to toxicity or symptomatic deterioration, or who have commenced subsequent anticancer therapy, will be followed up with tumor assessments until RECIST 1.1-defined PD plus an additional follow-up scan or until death (whichever comes first) and followed for survival.

8.2.7 Accountability and dispensation

All sites will keep drug accountability records during the study. At most sites, these records will be maintained and kept at the local pharmacy.

8.2.8 Disposition of unused investigational study drug

The site will account for all investigational study drug dispensed and appropriately destroyed. Certificates of delivery and destruction must be signed and reported to sponsor.

8.2.9 Monitoring of dose administration

According to local routines.

8.3 Thoracic radiotherapy

8.3.1 Timing

Ideally, patients randomized to the experimental arm are to receive TRT between the second and third chemo-immunotherapy course. TRT may start concurrently with the second course, and TRT should be completed before the third chemo-immunotherapy course commences.

However, there might be logistical challenges if chemo-immunotherapy courses are delayed due to toxicity from chemo-immunotherapy. In case, TRT may start after the second course even if the second course is delayed, but TRT may also start as scheduled regardless of the delay of the second chemo-immunotherapy course (i.e. 21-28 days after the first day of the first chemo-immunotherapy).

If TRT is delayed due to intercurrent disease prohibiting TRT starting as planned, TRT should be administered as soon as possible. If TRT is not administered, patients should still receive chemo-immunotherapy as scheduled.

8.3.2 TRT fractionation schedule

Patients should receive 30 Gy in 10 fractions, 5 fractions per week. The optimal treatment time is 12 days,

but up to 15 days is allowed in case of holidays or unplanned delays.

8.3.3 Treatment planning CT-scan

The treatment planning CT scan (or PET CT scan if that is the local routine) should be done with the patient immobilized in supine position according to local standard procedures for radiotherapy of the thorax. The whole thorax should be included in the CT scan and IV contrast should be used. Slice thickness should be \leq 3 mm. The use of 4DCT is recommended and breath-hold technique or gating is allowed, but not mandatory.

8.3.4 TRT guidelines in the CREST trial

The planning target volume (PTV) was defined as the post-chemotherapy volume with a margin of 15 mm. The initially positive hilar and mediastinal nodal stations were included, also in case of a complete response. The V_{20} should be <35% of the total lung volume. A lung correction was required for all treatment plans. All modern RT techniques (including IMRT and VMAT) were allowed. The definition of volumes and calculation of doses should be performed according to the ICRU.⁴⁸

8.3.5 Targets for TRT in the present trial

Preferably, the target volume should include the primary lung tumor and regional lymph node metastases identified before chemoimmunotherapy commenced, also in case of a complete response. Extensive, elective nodal irradiation is not allowed.

If possible, all thoracic lesions should be included in the radiotherapy field. If this is not possible, lesions compressing central airways or mediastinal structures (e.g. large vessels and nerves) should be prioritized. A minimum of one lesion should be irradiated. If a complete response is achieved by the time of the CT planning scan, this lesion may be a previously enlarged lymph node.

8.3.6 Delineation of target volumes

The gross tumor volume (GTV) will include the residual volume after the first (or second) chemoimmunotherapy course. The clinical target volume (CTV) will account for microscopic spread and is generated by expanding the GTV with 5 mm in all directions, but not across anatomic barriers such as trachea, heart, esophagus, bones, except when there is radiological invasion into these structures. The planning target volume (PTV) is defined by expanding the CTV with a margin defined according to local routines.

8.3.7 Delineation of organs at risk (OARs) and corresponding normal tissue dose constraints

In thoracic radiation the critical normal structures (organs at risk) that are likely to receive a significant radiation dose are: spinal cord; lungs; heart and pericardium; oesophagus. It is important to know the dose delivered to these structures, as this must be kept within normal tissue 'tolerance'. The following OARs should be contoured:

Organ at risk	Physical dose	Delineation
Lungs	Mean lung dose ≤12 Gy	Both lungs minus GTV (IGTV)
	V _{20 Gy} <30%	
	V _{5 Gy} preferably <55%	
Spinal canal	$D_{0.03 \text{ cm}3} \le 30 \text{ Gy}$	Contoured as the bony edge of
		the vertebral foramens from 2 cm
		above and below the PTV
Heart	V _{10 Gy} <10%	The whole heart below the
	Mean heart dose should be as low as possible	division of the truncus pulmonalis
Esophagus	D _{0.03 cm3} ≤ 30 Gy	From just below the larynx to the
	Mean esophageal dose should be as low as	gastric-esophageal junction

TRIPLEX 1.1 05-JAN-2022

possible. Hot spots in the esophagus should
be avoided.

8.3.8 Treatment planning

Megavoltage equipment with a nominal photon energy of 6 MV is recommended. Inverse planning techniques like intensity modulated RT (IMRT) and rotational techniques such as volumetric modulated arc therapy (VMAT) and modern dose calculation algorithms (Monte Carlo, AAA, Collapsed Cone etc) should be used. A dose calculation grid of 2 mm³ is recommended. A median dose of 30 Gy should be delivered to the CTV. 98% of the PTV should be covered by the 95 % isodose. In those parts of the PTV consisting of normal lung tissue, a coverage of the 90% isodose is sufficient. A near maximum dose (D_{2%}) of 107% is accepted.

8.3.9 Treatment

Daily cone beam CT (CBCT) with soft tissue match according to the target volume is mandatory.

8.3.10 Quality assurance of the thoracic radiotherapy

The first radiotherapy plan at each site should be sent to the central trial office in Trondheim as soon as possible. All radiotherapy plans will be reviewed by a study physician and a medical physicist, and feedback provided within 5 working days. When all patients have completed TRT, all radiotherapy plans should be sent to the central trial office for review.

8.3.11 TRT in the control arm

TRT may be offered patients in the control arm upon progression if this is considered the best alternative. Routine consolidation TRT after completion of chemoimmunotherapy is not allowed.

8.4 Prophylactic cranial irradiation (PCI)

PCI is not mandatory, but patients who respond to chemoimmunotherapy and have not previously received brain irradiation, should be offered PCI at the hospitals where this is established treatment of ES SCLC.

PCI should start between 4 to 6 weeks after the last chemoimmunotherapy course. PCI should be administered according to local routines. Hippocampus-sparing PCI is allowed. Recommended schedules are 25 Gy in 10 fractions or 30 Gy in 15 fractions. One schedule should be used for all patients at each site. PCI may be administered concurrently with durvalumab infusions.

8.4.1 Treatment of brain metastases

The treatment of brain metastases varies between hospitals. Patients with brain metastases may receive whole brain radiotherapy (WBRT) before or after chemoimmunotherapy. Recommended schedules are 30 Gy in 10 fractions (preferred) or 20 Gy in 4-5 fractions. WBRT should be administered according to local routines. WBRT may be offered patients who have received PCI if this is the local treatment policy.

An alternative to WBRT is stereotactic radiosurgery (SRS) provided the number, size and location of the brain metastases allows for SRS. The role of SRS in brain metastases from SCLC is less defined than for NSCLC, but especially for patients who have received PCI, have good and long extracranial disease control, and limited number of brain metastases, SRS may be a better alternative than WBRT. Surgery may be an alternative but is seldom offered SCLC patients.

Isolated progression in the brain does not necessarily warrant a change in systemic treatment provided local control is achieved by SRS, WBRT or surgery.

8.4.2 Irradiation of other lesions

Irradiation of other lesions is allowed according to each hospital's routines. This applies for both trial arms. If possible, it is preferred that any additional RT in the control arm is delivered after completion of chemo-immunotherapy.

8.5 Post study therapy

Upon progression, patients should be treated according to each hospital's routines. All post-study treatment, including all RT, should be recorded.

9. Treatment plan

9.1 Patient enrollment and randomization

9.1.1 Procedures for randomization

After patients are assigned a study ID and registered in the CRF, investigators randomize patients using the randomization module in the CRF. Patients will be randomized 1:1 in blocks of various sizes to receive chemo-immunotherapy alone or chemo-immunotherapy plus TRT stratifying for presence of liver metastases (yes vs. no), and presence of brain metastases (yes vs. no). The study is open label, and patients and investigators will know the results of the randomization. They will not, however, know the results of previous randomizations or the block sizes.

9.1.2 Procedures for handling patients incorrectly enrolled

Patients who are incorrectly enrolled and/or randomized will be discussed with the Chief Investigator before deciding whether the patient should be withdrawn. If there has been a major protocol violation, the patient will be withdrawn from the study.

10. Restrictions during the study and concomitant treatment(s)

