- Steroids as premedication for hypersensitivity reactions (e.g., CT scan premedication).
- 20. Receipt of live attenuated vaccine within 30 days prior to the first dose of IP. Note: Patients, if enrolled, should not receive live vaccine whilst receiving IP and up to 30 days after the last dose of IP.
- 21. Female patients who are pregnant or breastfeeding or male or female patients of reproductive potential who are not willing to employ effective birth control from screening to 90 days after the last dose of durvalumab monotherapy.
- 22. Known allergy or hypersensitivity to any of the study drugs or any of the study drug excipients.
- 23. Judgment by the investigator that the patient is unsuitable to participate in the study and the patient is unlikely to comply with study procedures, restrictions and requirements.

Procedures for withdrawal of incorrectly enrolled patients are presented in 9.1.2.

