7.3 Withdrawal of patients from study treatment and/or study

7.3.1 Permanent discontinuation of chemotherapy and durvalumab

Discontinuation of study treatment, for any reason, does not impact the patient's participation in the study. A patient who decides to discontinue IP should be asked about the reason(s) for discontinuation and the presence of any AE. The patient should continue attending subsequent study visits, and data collection should continue according to the study protocol. If the patient does not agree to continue in-person study visits, a modified follow-up must be arranged to ensure the collection of endpoints and safety information. This follow-up could be a telephone contact with the patient, a contact with a relative or treating physician, or information from medical records. The approach taken should be recorded in the medical records. A patient who agrees to modified follow-up is not considered to have withdrawn consent or to have withdrawn from the study.

Patients who permanently discontinue study treatment for other reasons than objective RECIST disease progression should be followed according to the study schedule similar to patients who are on study treatment.

All patients will be followed for survival until the end of the study. Patients who decline to return to the site for evaluations should be contacted by telephone if they agree.

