7.3.2 Lost to follow-up

Patients will be considered lost to follow-up only if no contact has been established by the time the study is completed, such that there is insufficient information to determine the patient's status at that time. Investigators should document attempts to re-establish contact with patients.

In order to support key end points of PFS and OS analyses, the survival status of all patients in the full analysis and the safety analysis sets should be re-checked, this includes those patients who withdrew consent or are classified as "lost to follow-up". For patients lost to follow-up, site personnel should check hospital records, the patients' current physician, and a publicly available death registry (if available) to obtain survival status.

If a patient has actively withdrawn consent to the processing of their personal data, the survival status of the patient can be obtained by site personnel from publicly available death registries (if available) where it is possible to do so under applicable local laws to obtain a current survival status.

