7.3.3 Withdrawal of consent

Patients are free to withdraw from the study at any time without prejudice to further treatment. Patients who withdraw consent for further participation in the study will not receive any further study treatment or further study observation, with the exception of follow-up for survival, which will continue until the end of the study unless the patient has expressly withdrawn their consent to survival follow-up. Note that the patient may be offered additional tests or tapering of treatment to withdraw safely.

A patient who withdraws consent may be asked about the reason(s) for withdrawal and the presence of any AE but does not have to give reasons for withdrawing. The Investigator will follow up AEs outside of the clinical study. If a patient withdraws consent, they will be specifically asked if they also withdraw consent to all further follow-up (e.g. survival contact phone calls).

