11.4.6 Withdrawal of informed consent for donated biological samples

If a patient withdraws, collection of data and biological material will stop, but according to Norwegian legislation, already collected data and material will be included in the analyses.

12. Disease evaluation and methods

The response to immunotherapy may differ from the typical responses observed with cytotoxic chemotherapy including the following (Wolchok et al 2009, Nishino et al 2013):

- Response to immunotherapy may be delayed
- Response to immunotherapy may occur after PD by conventional criteria
- The appearance of new lesions may not represent PD with immunotherapy
- SD while on immunotherapy may be durable and represent clinical benefit.

Based on the above-described unique response to immunotherapy and based on guidelines from regulatory agencies, e.g., European Medicines Agency's "Guideline on the evaluation of anticancer medicinal products in man" (EMA/CHMP/205/95/Rev.4) for immune modulating anticancer compounds, the study implements the following in addition to standard RECIST 1.1 criteria:

- PD must be confirmed after 4-6 weeks if study treatment continues beyond PD. If clinically significant
 deterioration occurs, a new CT scan should be performed earlier to ensure that patients are offered
 relapse treatment at a time when they still may benefit from other therapies.
- Patients may continue to receive durvalumab beyond confirmed PD in the absence of clinically significant deterioration and if investigators consider that patients continue to receive benefit from treatment.

Modification of RECIST as described may discourage the early discontinuation of durvalumab and provide a more complete evaluation of its antitumor activity than would be seen with conventional response criteria. Nonetheless, the efficacy analysis will be conducted based on the RECIST 1.1 criteria.

Of note, clinically significant deterioration which is not due to another known condition or intercurrent disease is considered to reflect a rapid tumor progression that necessitates treatment with anticancer therapy other than durvalumab or with symptomatic progression that requires urgent medical intervention (e.g. CNS metastasis, respiratory failure due to tumor compression, spinal cord compression).

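### Section 9.1.2 withdraws incorrectly enrolled, randomised patients from the study without keeping survival follow-up, in conflict with 7.3.1, 7.3.3 and 11.1.5

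*Protocol*

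**What the plan says.** Section 9.1.2 deals with patients who were incorrectly enrolled and/or randomised. Each case is first discussed with the Chief Investigator. The section then fixes the outcome for one group: "If there has been a major protocol violation, the patient will be withdrawn from the study". Section 7.2 makes this the rule that sites look up for such patients: "Procedures for withdrawal of incorrectly enrolled patients are presented in 9.1.2".

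The follow-up rules stand elsewhere:

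- Section 7.3.1: "All patients will be followed for survival until the end of the study". Section 11.1.5 repeats this, whatever further treatment is given.
- Section 7.3.1 also separates reduced follow-up from leaving the study: "A patient who agrees to modified follow-up is not considered to have withdrawn consent or to have withdrawn from the study".
- Section 7.3.3 ends study observation after withdrawal of consent, "with the exception of follow-up for survival, which will continue until the end of the study unless the patient has expressly withdrawn" consent to that follow-up.
- Section 7.3.2 asks for survival status to be re-checked for all patients in the full analysis and safety analysis sets, and says that this includes those who withdrew consent or are lost to follow-up.

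Section 11.4.6, headed as withdrawal of consent for donated samples, adds: "If a patient withdraws, collection of data and biological material will stop".

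**The concern.** Sections 7.3 and 11.1.5 keep survival follow-up going when treatment stops and even when consent is withdrawn. Section 9.1.2 does not. As written, a randomised patient who has refused nothing can be given less follow-up than a patient who has withdrawn consent.

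The primary endpoint is 1-year overall survival, so what may go unrecorded is the primary outcome itself. Under 9.1.1 the allocation is known to patients and investigators, so a withdrawal after randomisation is discussed by people who may know the arm. Such losses need not be balanced between arms or unrelated to prognosis. An analysis-set definition can be reworded before the analysis. A survival status that was not collected may not be recoverable.

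**Working it through.** The plan's sample-size figures are not in dispute here and no arithmetic applies. The check is to set the rules side by side.

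**1. Who is covered by 9.1.2?** Patients incorrectly enrolled and/or randomised. Some of them have therefore already been allocated to an arm.

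**2. Is withdrawal optional?** The first sentence leaves the decision open, after discussion with the Chief Investigator. The second closes it where there has been a major protocol violation: the patient is withdrawn.

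**3. Withdrawn from what?** The text says the study. Section 7.3.1 shows what that phrase means in this protocol. A patient who accepts only modified follow-up (by telephone, through a relative or treating physician, or from medical records) does not count as withdrawn from the study. By contrast, a patient who is withdrawn from the study is outside even modified follow-up. Section 9.1.2 has no survival exception of the kind written into 7.3.3.

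**4. Does another rule restore follow-up?**

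| Situation | Governing text | Survival follow-up |
|---|---|---|
| Stops treatment | 7.3.1, 11.1.5 | Continues for all |
| Withdraws consent | 7.3.3 | Continues unless expressly refused |
| Lost to follow-up | 7.3.2 | Status re-checked from records and registries |
| Incorrectly enrolled, major violation, treatment started | 9.1.2 against 7.3.1, 7.3.2 and 11.1.5 | Conflict; arguably re-checked through the safety set |
| Incorrectly enrolled, major violation, treatment not started | 9.1.2 against 7.3.1 and 11.1.5 | Conflict; not clearly in the re-check |

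For the fourth row, 14.2.1 defines the safety set as all patients who commence chemo-immunotherapy, so a treated patient falls within the sets named in 7.3.2. For the last row, the schedule in section 2 places randomisation in the screening column, before the first course at week 0. There is therefore an interval in which a patient is randomised but not yet in the safety set. Whether the full analysis set would include that patient cannot be read from section 14.2, which defines an efficacy set of eligible randomised patients and uses no set of that name.

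**5. Does the loss reach the primary analysis?** Section 14.2.2 bases it on all eligible patients who are randomised. A patient withdrawn under 9.1.2 because an entry criterion was not met is outside that set already. A patient who meets the criteria but was randomised in error (for example, with the wrong stratum recorded; the example is mine) still counts as eligible, and a missing survival status then enters the primary analysis. In both cases an analysis of every randomised patient is incomplete.

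**6. Which rule prevails?** No section says. Section 7.2 sends the site to 9.1.2 and not to 7.3.

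**The case against.** The strongest reply is that the gap is narrow, and much of that stands.

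- **Scope.** Section 9.1.2 is confined to incorrectly enrolled or randomised patients. A reader might infer that any randomised patient with a major violation during treatment is removed, or that a site may stop follow-up on its own. Neither is supported: the heading and first sentence set the limit, and the case goes to the Chief Investigator first.
- **The re-check.** The list in 7.3.2 is introduced as an inclusion and is not closed, so patients withdrawn by the trial are not shut out by going unnamed. With the safety set as defined, treated patients are arguably covered. It would be too strong to say that their deaths go unrecorded. What remains is two instructions that point in opposite directions, and the untreated patients.
- **Analysis set.** Ineligible patients are outside the primary set whatever happens to their follow-up. For them the cost falls only on a complete all-randomised analysis.
- **Section 11.4.6.** A reader might infer that withdrawing consent for samples alone ends survival follow-up. The section sits within biological sampling, its heading concerns donated samples, and 7.3.3 is the specific rule on consent. The sentence is loosely worded, but this is an ambiguity and not a second contradiction of equal weight.

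It can also be said that the sentences in 7.3.1 and 11.1.5 already cover all patients. They do in their wording, but both stand under headings about stopping or ending treatment, and neither mentions patients whom the trial itself withdraws. They make the conflict visible without settling it.

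**Conclusion.** The point holds for 9.1.2. The section requires withdrawal from the study for a defined group of patients who may already be randomised, keeps no survival follow-up, and conflicts with 7.3.1, 7.3.3 and 11.1.5. The exposure is clearest for patients withdrawn between randomisation and the first course. For treated patients it is a conflict that 7.3.2 arguably resolves in favour of follow-up.

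The consequence is possible selective loss of the primary outcome among patients who still count as eligible, and no complete analysis of all randomised patients. A reader might want to attach a number of percentage points of bias. The documents do not support one: they give no rate of such withdrawals, no split by arm and no prognosis for those affected. If the group is very small, the effect will be small too.

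The conclusion rests on reading withdrawal from the study as 7.3.1 uses it. If the sponsor means withdrawal from study treatment only, the text should say so. The change is worth making because it protects the primary endpoint and costs almost nothing.

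**What to change.** - **Section 9.1.2:** state that any randomised patient handled under this section stays in the study, in the allocated arm, for survival follow-up under 7.3, unless the patient expressly refuses it. Whether study treatment continues is a separate clinical decision that this point does not touch.
- **Section 7.3.2:** name patients handled under 9.1.2 in the survival re-check, including those who never started chemo-immunotherapy.
- **Section 11.4.6 (minor clarification):** limit the sentence to biological material and data derived from it, and refer to 7.3.3 for clinical and survival data.

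The cost is about three sentences in an amendment. There are no new visits and no change to the sample size.
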